11.1.7 Checks for Endpoints

The following checks will be performed on the dates indicated in the study schedule:

- Occurrence of pancreatic fistula
- Occurrence of postoperative hemorrhage
- intraabdominal fluid collections
- re-intervention rate
- re-operation rate
- nausea
- occurrence of cardiovascular events
- re-laparotomy

Confidential

EU trial No: 2023-503349-71-00/ TransNiDeG

Attachment 001 to SOP MW-009.001

Clinical Trial Protocol version 2.0 of 28-JUN-2023

Effective Date: 18-Mai-2022

Version 001

Page 40 of 69

- lymphadenectomy
- MTL-30 (Mortality, Transfer, Length of stay)

Furthermore, the days of hospital stay (calculated from the day of discharge) will be documented in the eCRF.

11.1.8 Questionnaires/Scores

The following questionnaires will be provided to the subjects on Day 30 (+/- 2 Days):

- EORTC QLQ-C30 (Quality of Life Questionnaire C30)
- EORTC QLQ-PAN26

The questionnaires are free of charge and will be provided by the Coordinating Investigator for the trial sites. This includes a reference to the evaluation methodology.

11.1.9 Histopathology

Histopathology as diagnosed during routine pathology workup.

11.1.10 AEs and SAEs

Refer to Section 12.

12 Safety Data Collection, Recording and Reporting

Safety data collection, documentation and reporting of adverse events will be performed according to the applicable laws and regulations (CTR, AMG, ICH Guideline E19).

Details regarding safety data documentation and reporting are specified in the Safety Management Plan (SMP) of this trial. The Investigator's Brochure for an unapproved investigational product or summary of product characteristics for an approved product will be used as reference documents referring to safety specifications.

The investigator will be provided with AE and SAE reporting forms by SZB and will receive training for AE/SAE definition, documentation and reporting. The AE/SAE documentation and reporting will be monitored on site.

12.1 Definitions

12.1.1 Adverse Event (AE)

Adverse event means any untoward medical occurrence in a subject to whom a medicinal product is administered and which does not necessarily have a causal relationship with this treatment.

A subject means an individual who participates in a clinical trial, either as recipient of an investigational medicinal product or as a control.

An investigational medicinal product (IMP) is a medicinal product, which is being tested or used as a reference, including as a placebo, in a clinical trial.

12.1.2 Adverse (Drug) Reaction (AR)

All noxious and unintended responses to a medicinal product related to any dose should be considered adverse drug reactions. The phrase „responses to a medicinal product“ means that a causal relationship between a medicinal product and an adverse event is at least a reasonable possibility, i.e., the relationship cannot be ruled out.

12.1.3 Unexpected Adverse (Drug) Reaction (UAR)

An adverse reaction, in which the nature or severity of the event is not consistent with the applicable reference safety information (e.g., Investigator's Brochure for an unapproved investigational medicinal product or package insert/summary of product characteristics for an approved product)

12.1.4 Serious Adverse Event (SAE) or Serious Adverse Reaction (SAR)

A serious adverse event or reaction is any untoward medical occurrence that, at any dose:

- Results in death
- Is life-threatening
- Requires inpatient hospitalization or prolongation of existing hospitalization
- Results in persistent or significant disability or incapacity, or
- Results in a congenital anomaly or birth defect,
- Is another, according to medical assessment, clinically relevant event.

- 'life-threatening' in the definition of 'serious' refers to an event in which the subject was at risk of death at the time of the event. It does not refer to an event, which hypothetically might have caused death, if it has been more severe
- In general, 'hospitalization' signifies that the subject has been detained (usually involving at least an overnight stay) at the hospital or emergency ward for observation and/or treatment that would not have been appropriate in the physician's office or outpatient setting. Complications that occur during hospitalization are AEs. If a complication prolongs hospitalization or fulfills any other serious criteria, the event is serious. When in doubt as to whether "hospitalization" occurred or was necessary, the AE should be considered serious
- In-patient stays without an underlying adverse event are not SAE (e.g.: elective in-patient treatment due to a pre-existing condition; inpatient admission for social reasons; admission to a rehabilitation clinic or hospice)
- The term disability means a substantial disruption of a person's ability to conduct normal life functions. This definition is not intended to include experiences of relatively minor medical significance such as uncomplicated headache, nausea, vomiting, diarrhea, influenza, and accidental trauma (e.g. sprained ankle) which may interfere or prevent everyday life functions but do not constitute a substantial disruption

Medical or scientific judgement should be exercised in deciding whether reporting is appropriate in other situations, such as important medical events that may not be immediately life-threatening or result in death or hospitalization but may jeopardize the subject or may require medical or surgical intervention to prevent one of the other outcomes listed in the above definition. These events should also be considered serious. Examples of such events are invasive or malignant cancers, intensive treatment in an emergency room or at home for allergic bronchospasm, blood dyscrasias or convulsions that do not result in hospitalization, or development of drug dependency or drug abuse.

12.1.5 Suspected Unexpected Serious Adverse (Drug) Reaction (SUSAR)

A SUSAR is an adverse reaction, which is suspected, serious and unexpected because the nature, severity or outcome of this event is not consistent with the applicable reference safety information (e.g. Summary of Product Characteristics for an authorized product or Investigator's Brochures for an unauthorized investigational medicinal product).

12.2 Criteria to be evaluated by the investigator (1st assessment)

By including the patient in the clinical trial and first administration of IMP, all adverse events (AEs), including intercurrent diseases, must be documented in the patient file and subsequently in the CRF. Disease signs, symptoms and laboratory changes should, as far as possible, be combined **into one single diagnosis**. The documentation of the event shall include the following criteria: "type", "beginning and end" and "outcome of the event" (recovered, improved, unchanged, recovered with sequelae, worsened death, unknown). The event is then evaluated according to the following criteria:

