The most frequent complication following pancreatoduodenectomy (PD) is delayed gastric emptying (DGE) with a reported incidence of 19%-57% [1]. A wide range of causative mechanisms has been proposed for DGE: the absence of hormonal stimulation due to the resection of the duodenum, ischemia of the stomach and duodenum following resection, denervation of the stomach and duodenum, post-operative pylorospasm, DGE secondary to other intraabdominal complications, pancreatic fibrosis, cholangitis, pancreatitis, alteration of the endocrinologic milieu or torsion/angulation of the reconstructed alimentary tract [2]. In fact, most studies concentrating on DGE accused technical aspects of the reconstruction to cause DGE, but none was able to ameliorate DGE. Neither ante- or retrocolic reconstruction route [3], pylorus resection and –preservation [4], nor single versus double loop reconstruction [5] does influence the frequency of DGE following PD. Often, DGE is self-limiting [2] and does not increase periprocedural mortality [6,7], but DGE is known to significantly increase hospital stay [8]. Recently DGE was described for the first time to negatively affect cancer specific survival [9]. So, strategies are needed for the treatment of delayed gastric emptying to increase the utilization of adjuvant chemotherapy with the goal of improved overall survival.

The aim of this clinical trial is to assess the effect of transcutaneous administered nicotine on the development and severity of delayed gastric emptying (DGE) following pancreatoduodenectomy (PD) as compared to placebo.

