6.2 Risk for study participant

Of all substances in tobacco smoke, nicotine is the most likely prokinetic substance [39]. This substance can easily and safely be applied through a nicotine patch. This standard therapy for smoking withdrawal is extremely safe in terms of adverse and serious adverse events [53]. The most frequent adverse event was skin irritation in about 25% of the patients (while 13% of the placebo group experienced skin irritation) [54]. Gastrointestinal symptoms are rare, with only 5% of the patients developing nausea (placebo 4%) and another 4% developing constipation, diarrhoea or dyspepsia (placebo 4%)[54].

The dosing of 14mg/24h seems safe even in non-smokers with only transient nausea as the only symptom [55]. Even in the elderly, no serious adverse events were noted with nicotine patch administration [56]. Non-ischemic chest pain and palpitations were reported, but were extremely rare [53]. There is no evidence, that nicotine replacement therapy increases the risk of heart attacks [53]. In a postsurgical setting, transdermal nicotine was examined in non-smokers in several studies addressing postoperative pain. In none of these, serious adverse events occurred [57,58]. Nicotine application was safe in terms of anastomotic healing and surgical site infections [59,60]. Even in critically-ill non-smokers, transdermal nicotine application was safe in terms of side-effects and adverse events [61]. The safety of transdermal nicotine in non-smokers was confirmed in a recent review [62].

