10.8 Dosage, Mode of Application and Dose Schedule of IMP

IMP patches will be applied by unblinded members of the investigator's team only.

Application on Day 1 will be done during or immediately after surgery. Application on Days 2 to 7 should be done preferably in the morning with an interval of approximately 24h (+/-6h) between treatments.

The dose of 14mg/24h for Nicotine patches was chosen as the medium dose for Nicotine patches being used for smoking cessation. This dose was proven safe even in non-smokers with only transient nausea as the only symptom [55] and in the elderly, where no serious adverse events were noted [63]. Also in critically-ill patients, a dosing of 14mg/24h was tolerated without relevant side-effects [61]. The dose was chosen to have most likely a significant effect without causing harm to the subjects.

According to the SmPC, the patch has to be placed either on the upper arm, upper hip or in the shoulder area. For standardization purposes in this study, the patches will be applied on the upper arm.

The patch should be placed on non-injured, clean and dry skin with as less hair as possible. The patch will be left on the application area for approximately 24 hours (+/-6h) after which the patch will be replaced by a new one. The application area has to be changed every day to avoid skin reactions. Therefore, it is preferred to change the arm for application every day.

After application of the Verum or Placebo patch, another patch has to be placed over the IMP patch to cover it for blinding purposes. This "blinding patch" has to cover the IMP patch totally. It has to be ensured that any manipulation of the "blinding patch" can be discovered.

Both patches (the IMP patch and the "blinding patch") must not be taken off during the time of application e.g. for taking a shower. Although the IMP patch is not water-resistant, it can be left on the skin when showering carefully.

The application and blinding process is described in detail in the IMP Manual.

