12.4 Documentation and Reporting of AEs, Follow-up

Any AE defined in clinical trial protocol as relevant for the evaluation and analysis of the clinical trial has to be documented in the CRF on the respective Adverse Event Report Form. Documentation and evaluation of each AE occurring between:

- the visit with the first administration of IMP to the subject and
- the visit of discharge.

According to the CTR, only adverse events and unexpected clinical diagnostic findings that are identified in the protocol as critical to safety evaluations must be reported by the investigator to the sponsor.

All medical conditions prevalent prior to study enrolment and all Adverse Events (AE) that occur after first dosing until discharge will be collected throughout the study and documented in the subject's medical record using medical terminology and transferred to the CRF. If applicable, AEs and SAEs that relate to any later protocol-specified procedure will be recorded. Furthermore, the investigator should report any SAE that occurs after these time periods and after end of the clinical trial, if the SAE is believed to be related to the study drug. An SAE report should be completed for any event where doubt exists regarding its seriousness. To ensure comparability of the safety data of the two study arms any adverse event in patients of the control arm will also be recorded although no study drug will be administered. Whenever possible, diagnoses should be given when signs and symptoms are due to a common etiology. All measures required for adverse event management must be recorded in the source document and reported according to sponsor's instructions. The investigator evaluates all Adverse Events regarding severity, causality as well as seriousness.

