12.5 Documentation and Reporting of SAEs

Every SAE will always be documented in the patient file and in the eCRF even if they are

- not severe
- meeting CTCAE grade 1 or 2
- not at least possibly related
- declared in the protocol as being exempt from reporting without undue delay, by the investigator to sponsor (refer to Section 12.5.1)
- primarily attributed to the underlying disease

Every SAE has to be reported immediately to the Sponsor Delegated Person/ Coordinating Investigator and SZB except those SAEs the protocol identifies as not requiring immediate reporting. However, **every SAE that is considered related to the IMP will always be reported to the Sponsor Delegated Person/ Coordinating Investigator without undue delay** According to the documentation of AEs any adverse event in patients of

the control arm meeting the criteria of an SAE will also be recorded although no study drug will be administered to ensure comparability of the safety data of the two study arms.

The documentation of the SAEs for a patient is carried out as described under 12.4, the reporting of SAEs for study patients is carried out within the following time periods:

- after the subject has been randomized and has received IMP for the first time
- up to 24h after the subject has received the last dose of IMP
- after these time periods until end of trial, when the SAE is believed to be related to the IMP
- after the end of trial when the investigator becomes aware of a SAE with a suspected causal relationship to the IMP

Any SAE occurred after application of study drug should be reported **immediately** after investigator awareness of the event to the sponsor (at the latest within 24 hours):

Study Coordinating Center of the SZB
Studienzentrale Studienzentrums Bonn (SZB)
[contact]
E-Mail: [contact]

Reporting should occur by fax on the **SAE report form** provided for this purpose. Symptoms, signs and laboratory changes should, as far as possible, be combined into one **single diagnosis**. The investigator is responsible for assessing the event (seriousness, intensity, causality). If necessary information is not fully available at this time, follow-up reports should be sent as soon as possible. Questions must be answered promptly. Further information and details how to report are described in the **Safety Management Plan**.

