12.5.1 Serious Adverse Events exempted from expedited reporting

According to the ICH Guideline E19² in certain situations selective safety reporting may be appropriate. This applies for example if the IMP has received a marketing authorization from a regulatory authority, the safety profile is well-known, the clinical pharmacology has been described and understood, post-authorization data is sufficiently available.

In this clinical trial the test-IMP has a marketing authorization for more than 30 years in Germany and a very well-know safety profile from a large number of post-authorization data [54]. The aim of this trial is to provide evidence of efficacy of nicotine treatment in patients suffering from DGE after PD.

Surgical resection is a pre-planned procedure and not considered as trial treatment. Therefore, complications from surgical resection (PD) from the date of surgery until the end of follow-up are not considered AEs/SAEs unless the complications are considered to be related to treatment with the IMP. Surgical complications will be documented in the eCRF and the patient file.

Furthermore, events that are probably related to the underlying disease are not considered as AE/SAE as long as the severity of the event is to be expected and not aggravated.

² ICH Guideline E19 on a selective approach to safety data collection in specific late-stage pre-approval or post-approval clinical trials (16-Mar-2023)

The underlying disease is a condition prior to inclusion in the clinical trial. Events that are probably related to the underlying disease are not considered as AE/SAE as long as the event and the severity of the event are to be expected and not aggravated.

The following events are most likely to occur after surgical resection or are most likely related to the underlying disease:

- Postoperative pancreatic fistula
- Relaparotomy
- Postoperative haemorrhage
- Insufficiency of the biliodigestive anastomosis
- Insufficiency of the GE (Gastroenterostomy)
- (Superficial) wound infections
- Intra-abdominal abscess
- Pleural effusion
- Pneumonia

In recent studies, nicotine application was extremely safe in terms of anastomotic healing and surgical site infections [59,60]

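### After Visit 1, nausea in the patch period is captured only as an AE and can be absorbed into DGE, so the by-arm nausea comparison can depend on the DGE result

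*Protocol*

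**What the plan says.** **Combining rule.** Protocol 12.2, on AEs: "Disease signs, symptoms and laboratory changes should, as far as possible, be combined" under a single diagnosis. Section 12.5 repeats this for SAE reports: "Symptoms, signs and laboratory changes should, as far as possible, be combined into one" diagnosis. Section 12.4 gives a narrower form: "Whenever possible, diagnoses should be given when signs and symptoms are due to a common etiology".

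**Exclusion.** Under 12.5.1, complications of the resection "are not considered AEs/SAEs unless the complications are considered to be related to treatment with the IMP". The list of typical events there does not name DGE, but the Introduction (Section 5) does call it a complication: "The most frequent complication following pancreatoduodenectomy (PD) is delayed gastric emptying (DGE").

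**What is expected of the patch.** Section 10.8 says of the chosen dose: "This dose was proven safe even in non-smokers with only transient nausea as the only symptom". Section 6.2 cites nausea in 5% with the patch and 4% with placebo, from outside this surgical setting. Section 10.4 lists nausea as a frequent reaction and vomiting as an occasional one.

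**Where nausea is collected.** Section 11.1.7 lists nausea among the endpoint checks. Footnote 3 of the schedule (Section 2) places it at Visit 1, the day of surgery, with no endpoint checks at Visits 1.2, 1.3 and 1.5 to 1.7 and other items only at Visits 1.4, 2, 3 and 4. Nausea is not a row of the DGE grading table (11.1.6). Vomiting/gastric distension is such a row, assessed at Visits 1.3, 1.7, 2 and 3, and is also a secondary endpoint over 21 days.

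**The concern.** Nausea is the expected effect of nicotine in non-smokers and may also accompany DGE. If a patient with nausea is judged to have DGE, the combining rule invites the investigator to record DGE alone, and 12.5.1 then takes DGE out of the AE data unless it is attributed to the IMP. After Visit 1 no other planned record of nausea exists in the patch period.

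The nausea AE table would then lean towards patients without DGE. Treatment is intended to change the size of that group, so the comparison would be conditioned on a post-randomisation efficacy outcome. Tolerability against placebo is a stated objective, and safety data also go to the DSMB at 50% enrolment (Section 13). Because this is a collection rule, nausea never written down cannot be recovered at analysis.

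**Working it through.** **1. The plan's own DGE figures.** From the table in 14.2.3, any DGE is (18 + 7 + 10)/88 = 39.8% in smokers and (54 + 30 + 15)/186 = 53.2% in non-smokers, which agrees with the 40% v 53% in 5.2. Refitting a proportional odds model to the table gives a log odds ratio of -0.433 (95% CI -0.930 to 0.063), OR 0.648, which agrees with the stated -0.43 and 0.65. The planning rates give any DGE = 0.25 + 0.15 + 0.10 = 50%. Taking 50% on placebo (odds 1) and OR 0.65, DGE on nicotine is 0.65/1.65 = 39.4%.

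**2. Full absorption (upper bound).** Let D be the DGE rate in an arm and q the nausea rate in patients without DGE, assumed equal in both arms (no true nausea effect). If all nausea in DGE patients is absorbed, the recorded rate is (1 - D) × q, and the ratio of nicotine to placebo is (1 - D_nic)/(1 - D_pla) for any q.

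| Scenario | DGE placebo | DGE nicotine | Recorded ratio |
|---|---|---|---|
| OR 0.65 | 50% | 39.4% | 0.606/0.500 = 1.21 |
| Retrospective rates | 53.2% | 39.8% | 0.602/0.468 = 1.29 |
| No DGE effect | 50% | 50% | 1.00 |
| DGE worsened, OR 1/0.65 | 50% | 60.6% | 0.394/0.500 = 0.79 |

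The protocol gives no nausea rate for this setting, so q is an assumption. In the first row, q = 10%, 20%, 30% and 40% give recorded rates (nicotine v placebo) of 6.1% v 5.0%, 12.1% v 10.0%, 18.2% v 15.0% and 24.2% v 20.0%.

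**3. Partial absorption.** Let a be the share of nausea in DGE patients that is absorbed. The recorded rate is D × q_D × (1 - a) + (1 - D) × q_N. Assume q_D = 80% with DGE, q_N = 20% without, and DGE 50% v 39.4%.

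| a | Placebo | Nicotine | Difference (points) |
|---|---|---|---|
| 0% (true) | 50.0% | 43.6% | -6.4 |
| 25% | 40.0% | 35.8% | -4.2 |
| 50% | 30.0% | 27.9% | -2.1 |
| 75% | 20.0% | 20.0% | 0.0 |
| 100% | 10.0% | 12.1% | +2.1 |

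The difference is (D_nic - D_pla) × [q_D(1 - a) - q_N], which is zero when 1 - a = 0.20/0.80, that is, a = 75%. The sign turns only above that.

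**4. Equal DGE, true nausea excess.** With DGE 50% in both arms, full absorption, nausea independent of DGE and true nausea 30% v 20%, the table shows 15% v 10%. The ratio stays at 1.5; the difference falls from 10 to 5 points.

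**5. Against sampling noise.** With 120 per arm and 12.1% v 10.0%, the standard error of the difference is √(0.121 × 0.879/120 + 0.10 × 0.90/120) = 0.040, or 4 points, against an artefact of 2.1 points.

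**The case against.** Several stronger readings are tempting, and the documents do not support them.

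- **That merging is compulsory.** The wording is advisory, and 12.4 ties it to a common etiology. Nausea that the investigator attributes to the patch need not be merged.
- **That DGE is declared not to be an AE.** This is inferred from the general exclusion; DGE is not named. Events judged related to the IMP remain AEs, and 12.2.3 counts a possible relationship as related.
- **That vomiting is lost too.** It is collected at four visits whatever the AE coding, though pooled with distension and itself part of the DGE grade.
- **That an effective patch will look worse on nausea.** Step 3 shows this needs heavy absorption when nausea is commoner in DGE, and step 4 shows that halving of an excess applies to the difference only.

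Two further objections carry weight. Grading in 11.1.6 starts from tube need at POD 4 or food intolerance at POD 7, so early transient nausea may be recorded before DGE is recognised. And details of safety documentation are deferred to a Safety Management Plan, which is not shown and may set conventions for single terms. Safety analysis is also descriptive only.

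These points limit the size of the problem without closing the route. The later patch days overlap with the emergence of grade A. A blinded investigator cannot readily tell patch nausea from DGE nausea, and 12.2.3 permits a not-related judgement when an underlying condition or intervention explains the event well enough. After Visit 1 nothing else in the protocol records nausea during the patch period.

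**Conclusion.** The point holds in a limited form. Read together, the combining rule, the exclusion of resection complications and the Visit 1-only nausea check allow nausea in DGE patients to leave the safety data, so the by-arm nausea comparison can depend on the DGE result.

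Neither size nor direction can be fixed from the protocol. Full absorption with no true nausea effect gives a spurious risk ratio of 1.21, or 1.29 with the retrospective rates; a harmful DGE effect gives 0.79, which could hide an excess; equal DGE and equal absorption give little or no bias in the ratio. The nausea and absorption rates are assumptions. In the worked example the artefact is smaller than one standard error, so this is a minor improvement to data collection and does not threaten the primary analysis.

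**What to change.** In 12.2, 12.4 and 12.5, exempt nausea from the single-diagnosis rule from Day 1 until the last patch is removed. Record it as its own item, with start and stop dates and intensity, in all patched patients whether or not DGE is graded, and tabulate it by arm in all patched patients. The simplest route is to extend the existing nausea check in schedule footnote 3 to Visits 1.2 to 1.7. The Day 7 patch stays on for about 24 hours after application, so the item also needs to cover the interval up to removal. Separately, state in 12.5.1 whether DGE counts as an AE, and align the Safety Management Plan.

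The cost is a few sentences, one added eCRF item at six visits and a fuller AE table, since post-operative nausea can be expected to be common in both arms.
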